- Hydration: Ensure adequate hydration (1.5 L to 2 L) 48 hours prior to initiating therapy with venetoclax and throughout the ramp-up period, especially on the first day of each ramp-up dose. Administer IV fluids as indicated based on the overall risk of TLS or for those who cannot maintain adequate oral hydration.
- Anti-hyperuricemic agents: Administer anti-hyperuricemic agents (e.g., allopurinol) within 72 hours prior to initiation of venetoclax; consider continuing through the ramp-up period. Rasburicase is recommended for subjects at high-risk, especially those with high tumor burden.
- Laboratory Assessments:
 - Pre-dose: Assess blood chemistries prior to initiating venetoclax to evaluate kidney function and correct pre-existing abnormalities. Reassess blood chemistries before starting each subsequent ramp-up dose of venetoclax.

- Post-dose: **For hospitalized subjects**, monitor blood chemistries 4 hours, 8 hours, 12 hours, 24 hours and, as needed, 48 hours after the venetoclax dose. **For outpatient subjects**, monitor blood chemistries at 6 to 8 hours and at 24 hours after the venetoclax dose. Electrolyte abnormalities should be corrected promptly (see [Appendix G](#)). **The next dose of venetoclax should not be administered until the 24 hour blood chemistry results have been evaluated.** The monitoring schedule should be followed in the Operations Manual ([Appendix K](#)) when starting each subsequent ramp-up dose. Refer to [Appendix G](#) for definitions of laboratory and clinical TLS.
- Subjects at low risk of TLS may have laboratory assessments conducted on an outpatient basis. If low risk subjects are hospitalized for logistical reasons, laboratory assessments will be conducted per the outpatient schedule.
- Hospitalization: Based on investigator assessment, subjects with a high-risk of TLS require hospitalization at the 20 mg and the 50 mg ramp-up doses of venetoclax for more intensive prophylaxis and monitoring. The timing of discharge from hospital will be decided based on investigator assessment of available data at that time. Consider hospitalization for subsequent ramp-up doses based on the reassessment of risk. Subjects at low risk of TLS may also be hospitalized, at the investigator's discretion. During the course of the study, the investigators and Sponsor will review TLS data to determine whether continued hospitalization of these subjects is warranted.

Ibrutinib

Dose Modification for Adverse Reactions

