Potassium \geq 0.5 mmol/L increase from prior value (even if potassium within normal limits [WNL])	
 • Recheck potassium, phosphorus, uric acid, calcium and creatinine in 1 hour STAT. If further \geq 0.2 mmol/L increase in potassium, but still $<$ upper limit of normal (ULN), manage as per potassium \geq ULN. Otherwise recheck in 1 hour. • Resume per-protocol testing if change in potassium is $<$ 0.2 mmol/L, and potassium $<$ ULN, and no other evidence of tumor lysis. • At discretion of Investigator, may recheck prior to hospitalization. If stable or decreased, and still WNL, hospitalization is at the discretion of the Investigator. Potassium, phosphorus, uric acid, calcium and • Creatinine must be rechecked within 24 hours.
Potassium $>$ upper limit of normal	
 • Perform STAT ECG and commence telemetry. • Nephrology notification with consideration of initiating dialysis. • Administer Kayexalate 60 g (or Resonium A 60 g). • Administer furosemide 20 mg IV \times 1. • Administer calcium gluconate 100 – 200 mg/kg IV slowly if there is ECG/telemetry evidence of life-threatening arrhythmias. • Recheck potassium, phosphorus, uric acid, calcium and creatinine in 1 hour STAT. 
 • If potassium $<$ ULN 1 hour later, repeat potassium, phosphorus, uric acid, calcium and creatinine 1, 2 and 4 hours, if no other evidence of tumor lysis.
Potassium \geq 6.0 mmol/L (6.0 mEq/L) and/or symptomatic (e.g., muscle cramps, weakness, paresthesias, nausea, vomiting, diarrhea)	
 • Perform STAT ECG and commence telemetry. • Nephrology (or other acute dialysis service) assessment with consideration of initiating dialysis. • Administer Kayexalate 60 g (or Resonium A 60 g). • Administer furosemide 20 mg IV \times 1. • Administer insulin 0.1 U/kg IV + D25 2 mL/kg IV. • Administer sodium bicarbonate 1 to 2 mEq/kg IV push. 
 • If sodium bicarbonate is used, rasburicase should not be used as this may exacerbate calcium phosphate precipitation. • Administer calcium gluconate 100 to 200 mg/kg IV slowly if there is ECG/telemetry evidence of life-threatening arrhythmias. Do not administer in same IV line as sodium bicarbonate. • Recheck potassium, phosphorus, uric acid, calcium and creatinine every hour STAT.

Abnormality	Management Recommendations ^{1,2}
Hyperuricemia	

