Uric acid \geq 8.0 mg/dL (476 μ mol/L)	
 Consider rasburicase (0.2 mg/kg as an intravenous infusion over 30 minutes). 
 If rasburicase is used, sodium bicarbonate should not be used as this may exacerbate calcium phosphate precipitation. Recheck potassium, phosphorus, uric acid, calcium and creatinine in 1 hour STAT.
Uric acid \geq 10 mg/dL (595 μ mol/L) OR Uric acid \geq 8.0 mg/dL (476 μ mol/L) with 25% increase and creatinine increase \geq 0.3 mg/dL (\geq 0.027 mmol/L) from pre-dose level	
 Administer rasburicase (0.2 mg/kg as an intravenous infusion over 30 minutes). 
 When rasburicase is used, sodium bicarbonate should not be used as this may exacerbate calcium phosphate precipitation. Consult nephrology (or other acute dialysis service). Recheck potassium, phosphorus, uric acid, calcium and creatinine in 1 hour STAT. If uric acid $<$ 8.0 mg/dL 1 hour later, repeat potassium, phosphorus, uric acid, calcium and creatinine 2 and 4 hours later, if no other evidence of tumor lysis.
Hypocalcemia	
Calcium \leq 7.0 mg/dL (1.75 mmol/L) AND Patient symptomatic (e.g., muscle cramps, hypotension, tetany, cardiac arrhythmias)	
 Administer calcium gluconate 50 to 100 mg/kg IV slowly with ECG monitoring. Telemetry. Recheck potassium, phosphorus, uric acid, calcium and creatinine in 1 hour STAT. If calcium normalized 1 hour later, repeat potassium, phosphorus, uric acid, calcium and creatinine 2 and 4 hours later, if no other evidence of tumor lysis. Calculate corrected calcium and check ionized calcium if albumin low.
Hyperphosphatemia	
Phosphorus \geq 5.0 mg/dL (1.615 mmol/L) with \geq 0.5 mg/dL (0.16 mmol/L) increase	
 Administer a phosphate binder (e.g., aluminum hydroxide, calcium carbonate, sevelamer hydroxide, or lanthanum carbonate). Nephrology (or other acute dialysis service) notification (dialysis required for phosphorus \geq 10 mg/dL). Recheck potassium, phosphorus, uric acid, calcium and creatinine in 1 hour STAT. If phosphorus $<$ 5.0 mg/dL 1 hour later, repeat potassium, phosphorus, uric acid, calcium and creatinine 2 and 4 hours later, if no other evidence of tumor lysis.

Abnormality	Management Recommendations ^{1,2}
Creatinine	

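### Appendix H: when the potassium ≥ 6.0 mmol/L (or symptomatic) row and the upper uric acid row are both met, the bicarbonate and rasburicase instructions cannot all be followed

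*Protocol*

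**What the plan says.** Four places in the protocol bear on this.

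- **Appendix H, Section 1, hyperkalemia.** The last row applies at potassium at or above "6.0 mmol/L (6.0 mEq/L) and/or symptomatic". Among its actions are "Administer sodium bicarbonate 1 to 2 mEq/kg IV push" and, directly beneath, "If sodium bicarbonate is used, rasburicase should not be used as this may exacerbate calcium phosphate precipitation".
- **Appendix H, Section 1, hyperuricemia, lower row** (uric acid ≥ 8.0 mg/dL). The wording is discretionary: "Consider rasburicase (0.2 mg/kg as an intravenous infusion over 30 minutes". If rasburicase is given, bicarbonate is ruled out.
- **Appendix H, Section 1, hyperuricemia, upper row.** This applies at uric acid ≥ 10 mg/dL, or at ≥ 8.0 mg/dL "with 25% increase and creatinine increase" of at least 0.3 mg/dL. Here rasburicase is to be administered, with no condition attached, followed by: "When rasburicase is used, sodium bicarbonate should not be used as this may exacerbate calcium phosphate precipitation".
- **Section 6.2, prophylaxis of tumor lysis syndrome (TLS).** "Rasburicase is recommended for subjects at high-risk, especially those with high tumor burden". The post-dose laboratory bullet then says "Electrolyte abnormalities should be corrected promptly" and sends the reader to Appendix G for this.

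The introduction to Appendix H presents the table as the minimum first response. It leaves later management to institutional practice once TLS has been diagnosed.

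**The concern.** Two rows of one table each call for a drug and each exclude the drug that the other row calls for. A subject can meet both rows at once, because potassium and uric acid are two of the four laboratory abnormalities in Appendix G and laboratory TLS requires at least two of them within 24 hours. Nothing in Appendix H ranks the rows.

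Prophylaxis opens a second route. A high-risk subject may already have received rasburicase under Section 6.2 before potassium reaches the threshold. Eligibility criterion 27, which excludes subjects with a contraindication to rasburicase, shows that its use is foreseen.

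The stake is safety conduct. In an acute event, site staff would find instructions that cannot all be carried out, and the Section 6.2 pointer would have taken them to an appendix that holds only definitions.

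**Working it through.** The plan states no figure on this point, so the check is one of logic. *Consistent* below means only that no written line is broken. It carries no clinical judgement.

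**Step 1. Write the instructions as constraints.** Let b = 1 if bicarbonate is given and r = 1 if rasburicase is given.

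1. Potassium row met: b = 1.
2. Upper uric acid row met: r = 1.
3. If b = 1, then r = 0 (potassium row).
4. If r = 1, then b = 0 (uric acid rows).

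The lower uric acid row sets no value of r, because it asks only for consideration.

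**Step 2. List the choices (b, r) that satisfy every constraint.**

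| Potassium row | Uric acid (mg/dL) | Consistent choices (b, r) |
|---|---|---|
| not met | < 8.0 | (0,0), (0,1), (1,0) |
| not met | 8.0 to < 10, without both rises | (0,0), (0,1), (1,0) |
| not met | ≥ 8.0 with 25% and creatinine rises | (0,1) |
| not met | ≥ 10 | (0,1) |
| met | < 8.0 | (1,0) |
| met | 8.0 to < 10, without both rises | (1,0) |
| met | ≥ 8.0 with 25% and creatinine rises | none |
| met | ≥ 10 | none |

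The contradiction is confined to the last two lines, where constraints 1 and 2 require b = r = 1 and constraints 3 and 4 forbid it.

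**Step 3. Rasburicase already given.** Suppose r = 1 from prophylaxis and the potassium row is then met, so b = 1 is called for. The exclusion in the potassium row looks forward only: no rasburicase once bicarbonate is used. The exclusion of bicarbonate after rasburicase stands in the uric acid rows. The text does not say whether it reaches rasburicase given earlier as prophylaxis, or for how long. If it does, no choice is consistent at any uric acid level. If it does not, the potassium row can be followed. This is a gap in the text rather than a proven contradiction. The same gap arises if rasburicase was given at discretion under the lower uric acid row.

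**Step 4. Rarity.** Protocol Section 2.1 reports, for the run-in of the reference study, one laboratory TLS event in 21 subjects and no clinical TLS: 1/21 = 4.8%. If that rate applied to 12 subjects (assumption), 12 × 1/21 = 0.57 laboratory TLS events of any kind would be expected. Four abnormalities form 4 × 3/2 = 6 pairs. One of the six is potassium with uric acid, and within that pair only the upper uric acid row conflicts. The 0.57 is a guide and not a strict bound, because the potassium row can also be met by symptoms alone and the route in Step 3 needs no second abnormality.

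**Step 5. Cross-reference.** The Section 6.2 post-dose bullet cites Appendix G for correcting electrolytes, and later in the same bullet cites it for TLS definitions. Appendix G contains only the definitions. The management table is in Appendix H, which the available protocol text names only in the list of appendices and in its own heading.

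**The case against.** The best reply is that the exclusions are matched warnings against giving the two drugs together. On that view the conditional *if* and *when*, and the appendix title, which speaks of recommendations, leave the choice to the clinician. Both rows involve nephrology or a dialysis service. Potassium above 6.0 mmol/L with uric acid above 8.0 mg/dL already meets the laboratory TLS definition, so the hand-over to institutional practice is close.

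This softens the conflict but does not remove it. The hand-over concerns ongoing management, while the clash lies in the first response, which the appendix describes as a required minimum. Where the authors intended discretion they wrote it in, as in the lower uric acid row. Neither row gives nephrology this decision. Even if a choice was meant, the text does not say which line yields.

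Timing also counts. Appendix J records that the primary analysis is complete, and Section 7.1 places that analysis after the last subject's Week 13 assessment or after all subjects have discontinued. The planned five-week ramp-ups are therefore probably over. What remains is re-initiation after an interruption and re-escalation after a reduction (Section 6.2), and ongoing dosing, for which Section 2 of Appendix H refers back to the same table. This lowers the urgency without correcting the text.

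Several stronger readings are not supported:

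- A reader might infer that any high uric acid conflicts with the potassium row. The plain ≥ 8.0 mg/dL row does not.
- A reader might infer that this is the typical TLS picture for which the table was written. The rows address single abnormalities, and most laboratory TLS pairs do not trigger the clash.
- A reader might take the 15 of 21 high-risk run-in subjects as the share exposed. That counts subjects in the category for which rasburicase is recommended. It does not count those who received it and then met the potassium row.
- A reader might infer that sites will act differently from one another. That is conjecture. The emergency wording in Appendix H refers to fast-rising potassium and not to this combination.

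**Conclusion.** The point stands in a narrow form. With the potassium row and the upper uric acid row both met, the instructions cannot all be followed, and Appendix H gives no precedence. Prior rasburicase is a related case that the text leaves open. The Section 6.2 pointer to Appendix G is a separate, plain clerical error.

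The documents give no frequency for the conflict itself. The nearest evidence, one laboratory TLS event in 21 subjects, suggests that it would be rare in a study of about 12. The finding concerns safety management only: endpoints, power and alpha are unaffected. It is worth correcting because the case is foreseeable and the correction is small.

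The conclusion assumes that the Operations Manual (Appendix K), which was not among the texts available, contains no precedence rule. Appendix H does not refer to it for one.

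**What to change.** 1. The sponsor's medical team should reconcile the potassium ≥ 6.0 mmol/L/symptomatic row, the upper uric acid row and the rasburicase bullet in Section 6.2. The text should state which instruction governs when both rows are met, and what applies when rasburicase has already been given, whether as prophylaxis or under the lower uric acid row. The clinical choice is theirs, and none is proposed here.
2. In the Section 6.2 post-dose bullet, change the reference for electrolyte correction from Appendix G to Appendix H. Keep Appendix G for the definitions.
3. Check that the Operations Manual agrees with the result.

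The cost is a few lines in a short protocol amendment, with the ethics committee review that Section 8.1 requires. No SAP change, new data or re-analysis is needed. The current protocol version already corrected a calcium threshold in Appendix G, so the TLS appendices are still being maintained.

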APPENDIX I. COVID-19-RELATED INSTRUCTIONS

Instructions related to the COVID-19 pandemic are listed below.

Benefits and Risks to Subjects

Considering the coronavirus (COVID-19) pandemic, the benefit and risk to subjects participating in this study has been re-evaluated. Subjects receiving venetoclax and ibrutinib may be at an increased risk for COVID-19 infection or experience serious illness if infected. Management of these AEs will be made on a case-by-case basis with consideration of benefit/risk by the investigators. However, based on the population, the disease being studied, and the anticipation that COVID-19-related risks are unknown between study subjects and the broader population of subjects receiving treatment for mantle cell lymphoma, no known change to the benefit/risk balance for subjects in this study is expected.

Refer to Section 5.1 for COVID-19 specific eligibility criteria.

Study Subject Information and Informed Consent

Due to the COVID-19 pandemic, it is possible that additional protocol modifications not outlined in this protocol may become necessary. If this situation arises, in addition to the study informed consent, additional verbal consent may be obtained prior to these adaptations or substantial changes in study conduct in accordance with local regulations. An appropriately signed and dated informed consent form should be obtained from the subject afterwards, as soon as possible.

COVID-19 Pandemic-Related Acceptable Protocol Modifications for Study Procedures

During the COVID-19 pandemic, if it is not possible for all study procedures to be performed as specified due to travel restrictions or other reasons, the following modifications are allowed:

- Some study visits and/or activities (e.g., physical examination, vital signs, ECOG) may be performed by phone/virtually. Refer to the sections below for further details.
- Some study visits and/or activities (e.g., ECG) may be performed by a local clinic/hospital/laboratory. These study visits and/or activities are listed in the operations manual under 'Local Labs & Exam'. All procedures performed at local facilities must be performed by appropriately qualified personnel.
- Some study visits cannot be performed locally or virtually and can only be performed at the central lab (e.g., PK and MRD assessment). Refer to the sections below for further details.
- Study Visits and/or activities should be performed as scheduled whenever possible. If it is not possible to do so due to the pandemic, the following modifications are allowed:
 - If an activity is missed during a virtual visit, perform the activity at the earliest feasible opportunity. Laboratory draws must be obtained within 24 hours from the scheduled visit.

Study procedures to be Completed at the Site at Next Feasible Visit

In the event sample collections may not be performed at the primary research site due to study modifications related to the COVID-19 pandemic the following procedures can be completed at the next earliest feasible visit:

- PK assessments
- Biomarker sample collection
- ECG (If necessary, the 12-lead ECG may be completed at an alternative local facility)
- PET/CT (or MRI) scan (If necessary, the PET/CT [or MRI] scan may be completed at an alternative local facility)
- Endoscopy (If necessary, the endoscopy may be completed at an alternative local facility)
and/or
- Disease assessments

The study site will use CB Trial Laboratory provided supplies and collect PK and biomarker samples as detailed in the CB Trial Laboratory Manual. These samples must be collected only after proper dosing and other specific requirements per the protocol have been met. If a subject is unable to go on-site for these samples due to COVID-19, these samples may be delayed until the subject is able to return to the study site at a later date, following proper dosing and other requirements per-protocol.

Study Procedures that can be Completed virtually via Phone or Video Conference due to COVID-19

If permitted by local regulations, the IRB/IEC, and the subject, some study visits may be conducted via phone or video conference if disease assessment is not required, and no dose modifications are anticipated. In these situations, vital signs may be obtained by the subject or caregiver as needed.

The physical examination can be performed via video, if possible. If not possible, the examination can be completed at the next visit when the subject is able to go to the site or can be completed by the subject's local physician. If subject has a home blood pressure and pulse kit and weight scale, subject may report these readings over the phone or via video. In these situations, height and weight may be performed by the subject or caregiver as needed. Additionally, the procedures outlined below can be conducted over the phone or via video.

Adverse event and ECOG assessment can be done over the phone or via video.

Clinical Laboratory Tests

If travel restrictions or other changes in local regulations in light of the COVID-19 pandemic prevent the subject from having blood drawn for laboratory testing at the study site, if possible, arrange for subjects to have laboratory work done at a local lab, hospital, or other facility. Local laboratory results should be obtained along with reference ranges and kept within the subjects' source documentation. The investigator should review local laboratory results as soon as possible.

The investigator or designee should confirm with the subject when the lab samples were collected.

Once subject is on a stable dose of venetoclax and ibrutinib for at least 4 weeks, if safety laboratory samples cannot be obtained, study drug administration may be continued provided the investigator has reviewed all prior laboratory results within 4 weeks and confirms and discusses with the subject that there is no safety concern for the subject to continue use of the study drug in the absence of current

labs. The subject should be scheduled for laboratory draws as soon as feasible within 3 days from the scheduled visit.

Urine pregnancy tests can be done at a local lab or test kits can be shipped by site staff to the subject. Home pregnancy tests should be performed monthly, regardless of ability to obtain other laboratory testing.

Withdrawal of Subjects and Discontinuation of Study: COVID-19 Pandemic-Related Acceptable Protocol Modification

During the COVID-19 pandemic, it has been necessary to employ mitigation strategies to enable the investigator to ensure subject safety and continuity of care. Acceptable mitigation strategies are identified and included in the Operations Manual in [Appendix K](#).

The investigator should contact the Sponsor medical contact before discontinuing a subject from the study for a reason other than described in the protocol to ensure all acceptable mitigation steps have been explored.

Interruption/Discontinuation of Study Drug Due to COVID-19 Infection

During the Study Drug Dosing Period, a subject with confirmed (viral test positive) or suspected COVID19 infection can only be dosed with study drug(s) if the following COVID-19 viral clearance criteria are met:

- At least 10 days since first positive test result have passed in asymptomatic patients or at least 10 days since recovery, defined as resolution of fever without use of antipyretics and improvement in symptoms.

Delays in study drug dosing due to the above COVID-19 testing guidance for subjects must be discussed with the AbbVie medical contact, along with the possibility of premature discontinuation from the study drug dosing period. Follow Section [5.6](#) for subjects who discontinued study drug. Frequency or timing of COVID-19 testing and intervals between testing for the above viral clearance criteria may be adjusted to account for epidemiologic trends, updated information regarding infectivity, and local/institutional guidelines.

Direct-to-patient Study Drug Shipment

If a subject is unable to come to the study site to pick up their study drug due to COVID-19, a direct-to-patient (DTP) study drug shipment can be made from the study site to the subject if allowed by local regulations. AbbVie will submit any required notifications to the regulatory authority as applicable.

The following DTP criteria must be met:

- Direct-to-patient (DTP) shipment of study drug is allowed by local regulations and the relevant ethics committee
- Study drug can be administered by the subject (or subject's caregiver) at home
- Subject agrees to have the study drug shipped directly to their home
 - Shipments may also include other study supplies (e.g., drug dosing diaries, paper copies of the patient-reported outcomes). Instructions will be provided by AbbVie as to how a study

site can initiate a DTP shipment using Marken, a global vendor selected by AbbVie to provide this service when necessary. Shipments of study drugs from the study site to a subject's home will be appropriately temperature controlled (qualified shipper or temperature monitoring) within the labeled storage conditions. Signature is required upon delivery; due to COVID-19-related social distancing, this may be provided by the courier after delivery. Documentation of the shipment is to be retained by the clinical site.

- AbbVie will not receive subject identifying information related to these shipments, as the site will work directly with the courier.

The study site is responsible for meeting IRB/IEC reporting requirements related to DTP shipments of study drug, and for obtaining consent to provide delivery information to the courier and documenting this consent in source documents.

Ethical Conduct of the Study

Investigators should notify AbbVie if any urgent safety measures are taken to protect the subjects against any immediate hazard.

Source Documents and Case Report Form Completion

During the COVID-19 pandemic, remote data review/verification may be employed if allowed by the local regulatory authority, IRB/IEC, and the study site.

Supplemental study case report forms should be completed in the event of COVID-19-related missed/virtual visits, study drug interruptions or discontinuations, or adverse events (including capture of specific signs/symptoms of infection and testing results).

Severe acute respiratory syndrome coronavirus 2 (SARS-CoV-2) infections should be captured as adverse events. If the event meets the criteria for a SAE, then follow the SAE reporting directions per the protocol. The following COVID-19-related supplemental eCRFs should be completed (for both serious and nonserious events of SARS-CoV-2 infections):

- COVID-19 Supplemental Signs/Symptoms
- COVID-19 Status Form

If a subject has a confirmed or suspected SARS-CoV-2 infection and study drug was interrupted, the investigator should contact the Sponsor emergency medical contact listed above before reintroducing study drug.

Reactions known to be associated with the SARS-CoV-2 vaccine should be reported as adverse events. If the event meets the criteria for an SAE, then follow the SAE reporting directions. All adverse events associated with the SARS-CoV-2 vaccine will be linked to the vaccine on the COVID-19 Vaccine eCRF.

COVID-19 Pandemic-Related Vaccination Guidance

Given the ongoing COVID-19 pandemic, selected non-live vaccines (e.g., messenger Ribonucleic acid [mRNA], non-replicating viral vector, protein subunit, etc.) to prevent SARS-CoV-2 infection may be

administered during screening or the treatment period, as long as components of the vaccine are not contraindicated.

The decision to receive a locally available vaccine should be based on local guidance and an individual discussion between the treating physician and the subject.

The potential impact of venetoclax and ibrutinib on SARS-CoV-2 vaccination is unknown and there is no restriction related to the administration of study drugs in this study.

Note: The above guidance applies to all SARS-CoV-2 vaccine doses given as part of the complete vaccination course.

These recommendations may be subject to change based on the evolving knowledge around the use of SARS-CoV-2 vaccines in patients with mantle cell lymphoma and as more data are collected in real-world scenarios and clinical trials.

Any SARS-CoV-2 vaccine information must be documented on the COVID-19 vaccine eCRF. Refer to the 'Source Documents and Case Report Form Completion' section of [Appendix I](#) for instructions on reporting any adverse events associated with the COVID-19 vaccine.

[COVID-19 Vaccine-related Lymphadenopathy and FDG PET/CT Timing](#)

Transient flurodeoxyglucose (FDG) uptake in normal or enlarged axillary, supraclavicular, and cervical lymph nodes have been reported after an ipsilateral deltoid vaccination. This phenomenon may confound interpretation in oncology patients undergoing FDG PET/CT. It is recommended to consider influence of the COVID-19 vaccination to PET/CT, this includes leaving an interval of 4-6 weeks after inoculation by the Japan Cancer Treatment Society.

Given increased immunogenicity of mRNA vaccines and to allow resolution of lymphadenopathy, the optimal timing for disease assessment is 4-6 weeks after COVID-19 vaccination. Although, vaccine-related lymphadenopathy and FDG uptake on PET/CT can mimic cancer and lead to confounding imaging results in some cases, it is reported that PET/CT should **not** be delayed when clinically indicated to be performed sooner.³⁵⁻³⁷

As per the discussion with AbbVie's internal study team, we propose the following strategies to be followed for the Disease Assessments:

- Please schedule the study visits including the PET/CT imaging and the Disease Assessments as outlined in [Appendix E](#) and the Operations Manual.
- If a COVID-19 vaccination (1st or 2nd dose) is also scheduled around the same time as of the scheduled study visits, it is preferable that the vaccine to be injected after all the study procedures including the PET/CT scans have already been performed.
- If a Disease Response assessment shows Partial remission, Stable Disease, or Disease Progression after COVID-19 vaccination, the Sponsor may ask investigator to perform confirmatory PET/CT scans to determine the validity of this assessment.

These recommendations may be subject to change based on the evolving knowledge around the use of SARS-CoV-2 vaccines in patients with relapsed/refractory Mantle Cell Lymphoma and as more data are collected in real-world scenarios and clinical trials.

Any SARS-CoV-2 vaccine information must be documented on the COVID-19 vaccine eCRF. If you have any questions, please do not hesitate to contact your responsible CRA or the study Medical Monitor/Therapeutic Area Medical Director.

